[upišite ovdje]

TIVA With Ketofol Versus Lidoketofol for Short-term Anesthesia on
Pediatric Patients; Effects on Recovery

18. December 2020.

METHODS

Patients

Randomized, prospective study will be performed between July 2020 and November 2020.

Two hundred pediatric patients aged 1–12 years with an American Society of Anesthesiologists status of I to II, schedule for elective short-term surgery, will be recruited. Hundred will be in the ketofol group and hundred in lidoketofol group. Demographic data including age and sex and also the duration of anesthesia in the two groups will be similar. The children will not be premedicated. If an intravenous (IV) cannula will not be inserted preoperatively, anesthesia will be induced with 4–5% sevoflurane via a face mask. After that, the sevoflurane will be stopped and induction drugs will be administered intravenously.

Intraoperative monitoring

Electrocardiogram (ECG), non-invasive arterial blood pressure, and peripheral oxygen saturation (Draeger-Perseus A500 Anesthesia Device Monitor, Draeger Medical Systems, Inc., Denver, MA) will be used for standard monitoring. A bispectral indeks monitoring system (BIS; BIS™ Brain Monitoring System, Covidien, San Jose, CA) will be used to measure depth of anesthesia. Systolic blood pressure (SBP), mean arterial blood pressure (MAP), diastolic blood pressure (DAP), heart rate (HR), and BIS values will be recorded at 5-min intervals during anesthesia.

Study design

The patients will be randomly allocated into two groups, via a computer-generated randomization list. Ketofol and lidoketofol will be prepared in one syringe. A Draeger™ Module DPS syringe pump (Draeger Medical Systems, Inc., Denver, MA) will be used for infusion of the ketofol and lidiketofol mixture. On arrival at the operating room, standard anesthetic monitoring including non-invasive blood pressure, electrocardiogram and pulse oximeter will be applied. General anesthesia will be induced by ketofol or lidoketofol and fentanyl, and after 20 s, the LMA will be inserted [13]. Mechanical ventilation will be performed to maintain the ET-CO₂ between 35–45 mmHg. Maintenance of anesthesia will be done using air/oxygen (50%/50%) and infusion of ketofol or lidoketofol. Randomization will be performed by random blocks (n=4). Ketofol will be prepared at ratio of 1:4 for induction and 1:7 for maintenance.

[upišite ovdje]

Lidoketofol group will be prepared with ketofol at same ratio plus lidocaine. Extubating time will be defined as the time between discontinuation of the infusion and extubation. The LMA will be removed when spontaneous regular breathing was confirmed. Children will be transferred to the PACU, where respiratory, heart rate and peripheral oxygen saturation (SpO_2) will be recorded. The length of staying in PACU will be defined as time between arrival and discharge time. All patients will be observed for 24 h postoperatively, and will be closely followed for propofol infusion syndrome (PRIS).

Primary and secondary outcomes

The primary outcome of this study will be extubating time. Secondary outcomes will be time spent in the PACU and total opioid consumption.

Statistical analysis

The data will be analyzed using Statistical Package for the Social Sciences software, version 24.0 (SPSS Statistics for Windows IBM Corp, Armonk, NY). Distributions of quantitative data will be described by medians and interquartile ranges, whereas absolute rates and percentages will be used to describe categorical data. Differences in median values of quantitative variables between the groups of patients will be tested with Mann–Whitney U test. The chi-square test will be used for the statistical analysis of the categorical data. All values of $P < 0.05$ will be considered to indicate statistical significance.

Results

Extubating time was significantly lower in lidoketofol group than in ketofol group (120 s versus 240 s; $p < 0.00001$). Length of stay in the PACU was lower in lidoketofol group than in ketofol group (20 min vs. 35 min; $p < 0.00001$). Fentanyl (2,1 μg per kg vs. 2,3 μg per kg; $P < 0.0056$) and propofol (6,6 mg per kg vs. 7,6 mg per kg; $P < 0.032$) consumption per kg were significantly lower in lidoketofol group.

[upišite ovdje]

Human Subjects Board Status: Approved Approval Number: 2181-147-
Review: 01/06/M.S.-20-12

Board Name: Etičko povjerenstvo
Board Affiliation: Klinički bolnički centar
Split [contact] Email:
[contact] Address:
KBCSplit
[name]
Split
Hrvatska

University Hospital of Split

Split, Croatia, 21000

Contact: [name]

[name], Mr.sc.MD [name] [contact]

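### The text is dated after its study window and already holds Results, so alone it cannot show pre-specification; it also calls propofol per kg significant though no outcome list includes it

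*Combined protocol and SAP*

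**What the plan says.** Everything is in the combined protocol and SAP.

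- **Timing.** The title block carries the date "18. December 2020". The Patients section says: "Randomized, prospective study will be performed between July 2020 and November 2020".
- **Outcomes.** The section on primary and secondary outcomes names extubating time as primary. For the rest it says: "Secondary outcomes will be time spent in the PACU and total opioid consumption". Propofol use does not appear.
- **Tests.** The Statistical analysis section says: "Differences in median values of quantitative variables between the groups of patients will be tested with" the Mann–Whitney U test. It then counts every P value below 0.05 as significant. Neither statement is confined to the listed outcomes.
- **Results.** The same text reports findings. The first begins: "Extubating time was significantly lower in lidoketofol group than in ketofol group". PACU stay follows. The last sentence joins fentanyl per kg with "propofol (6,6 mg per kg vs. 7,6 mg per kg", P < 0.032, and concludes for both that "consumption per kg were significantly lower in lidoketofol group".

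**The concern.** A plan supports a confirmatory reading only if it can be shown to predate sight of the data. This text is dated after the window in which the study was to run, and it reports the findings, so it cannot serve as that evidence by itself. What is at stake is how the three listed outcomes may be described, as pre-specified or as not shown to be so. Their numerical values are not in question.

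The propofol comparison raises a narrower issue. It shares one sentence and one significance statement with fentanyl, which is the measure reported for a listed secondary outcome. A reader who does not go back to the outcome list would give both the same standing.

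**Working it through.** No sample-size or power figure is involved. The check is a date difference and a comparison of two lists.

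**1. Dates.** Inputs: the title-block date (18 December 2020) and the window in the Patients section (July to November 2020).

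- Latest possible end of window, 30 November 2020, to 18 December 2020: 18 days.
- Earliest possible start, 1 July 2020, to 18 December 2020: 30 + 31 + 30 + 31 + 30 + 18 = 170 days.

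The date falls after the window on any reading of it. The Results section settles the point independently of the date: text that contains group values and P values was completed after those values were known.

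**2. Reported comparisons against listed outcomes.**

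| Reported in Results | Lidoketofol vs ketofol | Printed P | Listed outcome it matches |
|---|---|---|---|
| Extubating time | 120 s vs 240 s | < 0.00001 | Primary |
| PACU stay | 20 min vs 35 min | < 0.00001 | Secondary |
| Fentanyl per kg | 2.1 vs 2.3 μg per kg | < 0.0056 | Secondary (opioid consumption) |
| Propofol per kg | 6.6 vs 7.6 mg per kg | < 0.032 | None |

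Four comparisons are reported against three listed outcomes, and propofol is the one without a match. It is not an opioid, so the opioid outcome does not cover it.

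**3. Size of the propofol difference.** 7.6 − 6.6 = 1.0 mg per kg, and 1.0 / 7.6 = 13.2% of the ketofol value. The Results give no measure of spread and no interval, so the precision of this difference cannot be taken from the text.

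**4. Does propofol depend on how the four reported tests are treated?** The printed bounds are treated here as the P values.

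- Bonferroni over four tests: 0.05 / 4 = 0.0125. Propofol at 0.032 does not meet it; the other three do.
- Holm, smallest P first: thresholds 0.05/4 = 0.0125, 0.05/3 = 0.0167, 0.05/2 = 0.025 and 0.05/1 = 0.05. The ordered values 0.00001, 0.00001, 0.0056 and 0.032 all pass.

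The plan names neither procedure and defines no set of tests. The status of propofol therefore depends on a choice the plan did not make, while the three listed outcomes pass either way.

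**The case against.** The strongest reply is that the propofol sentence follows the plan. The test rule covers quantitative variables in general and the 0.05 rule covers all P values, so calling propofol significant breaks nothing written. The Results never call it an outcome, and as a component of the study mixture its dose per kg can be read as a description of exposure. It also passes Holm among the four reported tests. All of this stands. The fault is that the rule gives an unlisted comparison the same wording as a listed one, and the Results carry no label to tell them apart.

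On timing, the date may mark a later version or an upload, and the Methods may be carried over from an earlier approved plan. That also stands, and it is why the point is limited to what this text can show alone. Title and signature pages were removed from the copy reviewed, so nothing is made of version or approval details that it lacks.

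Three stronger readings are tempting and are not supported:

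- A reader might infer that the outcomes were chosen after the data were seen. The text shows when this version was completed, not when the outcomes were chosen.
- A reader might infer that propofol was picked from a larger set of tests, since the plan also collects monitoring data ("heart rate (HR), and BIS values will be recorded at 5-min intervals during anesthesia"). The documents do not say that these variables were compared between groups, so no number of hidden tests can be assumed.
- A reader might infer an outcome switch because total opioid consumption is reported as fentanyl per kg. The plan fixes no scale for that outcome, so this is an unstated unit and not a demonstrated change.

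**Conclusion.** The point holds in two limited parts.

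First, this version was completed with results in hand and is dated 18 days after the latest end of its study window. By itself it cannot verify that the outcomes and tests were pre-specified. It does not show the opposite, and it contains nothing that contradicts the primary or secondary results. Extubating time and PACU stay are reported as listed.

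Second, one of four reported comparisons, propofol per kg (a difference of 1.0 mg per kg, 13.2%), is on no outcome list and should be read as exploratory with a nominal P value. This is not a finding that the propofol result is false.

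The conclusion rests on the title-block date, the presence of the Results, and the outcome list as printed. An earlier dated version listing these outcomes and tests would resolve the first part. It would resolve the second only if it also listed propofol. The point should be fixed, but it changes no primary estimate or test.

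**What to change.** 1. In the Results, separate propofol per kg from fentanyl. Label it an unlisted, exploratory comparison, report the difference with a confidence interval computed from the patient data (a Hodges–Lehmann shift estimate would match the Mann–Whitney test), and describe its P value as nominal.
2. State in the document that this version was completed after results were available, and keep the Results visible.
3. Cite the version approved before recruitment if it lists these outcomes and tests. If it does not, or none can be produced, label the affected comparisons as not shown to be pre-specified.

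The cost is small: one interval from data already collected, a version statement and some rewording, with no new patients or measurements. The downside is that the propofol claim becomes exploratory. If no earlier version can be cited, the listed outcomes also carry the qualification in step 3.

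### Children without a cannula get sevoflurane before the randomised drug, but route is neither a stratum nor an analysis factor, so the trial cannot show whether its recovery result holds in TIVA-only children

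*Combined protocol and SAP*

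**What the plan says.** The title sets the question as "TIVA With Ketofol Versus Lidoketofol for Short-term Anesthesia on" paediatric patients, with recovery as the target. Under METHODS, Patients, there are two ways into anaesthesia. The rule for a child with no cannula is: "If an intravenous (IV) cannula will not be inserted preoperatively, anesthesia will be induced with" 4–5% sevoflurane by mask. The next sentence fixes the order: "After that, the sevoflurane will be stopped and induction drugs will be administered intravenously". No duration of sevoflurane, end-tidal level or interval before the study drug is stated.

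Study design describes induction a second time. It names only the study mixture and fentanyl and does not mention the sevoflurane route. Maintenance is air and oxygen plus the study infusion, with no volatile agent named.

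Allocation is 1:1: "Hundred will be in the ketofol group and hundred in lidoketofol group". The list is computer-generated in blocks of 4, and no stratification factor is named.

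Under Primary and secondary outcomes, "The primary outcome of this study will be extubating time"; Study design defines it as running from the stop of the infusion to extubation. Statistical analysis plans an unadjusted Mann–Whitney U test for quantitative variables, with no covariate, stratum or sensitivity analysis. Results gives 120 s versus 240 s for the primary outcome and no count or split by induction route.

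**The concern.** The outcome is an emergence time after short procedures. Sevoflurane given at the start could in principle carry over into emergence, or alter how much study mixture and fentanyl is used. Children induced by mask have had a different anaesthetic technique from those induced intravenously throughout, and the plan analyses the two as one group without saying how many of each there are.

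Two things are at stake. The first is interpretation: a reader who wants the TIVA answer promised by the title cannot extract it, because neither the mix of routes nor the result within each route is available. The second is precision: if route affects recovery time, leaving it out of the analysis adds between-child variation that a stratified comparison would remove.

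**Working it through.** The plan offers no figure to reproduce on this point. The total of 200 is stated without effect size, SD or power. The calculations below only gauge size.

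**Inputs from the document:** 100 children per arm (Patients); no stratum (Study design); medians of 120 s and 240 s, a difference of 120 s (Results).

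**Assumptions, not in the document:** share of mask inductions p = 20% to 50%; carry-over of 30 to 120 s per exposed child, with 240 s as a harsher case; two-sided alpha of 0.05; route unrelated to arm.

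**1. Chance imbalance in route.** SE of the between-arm difference = √(2p(1−p)/100).
- p = 0.2: √(2 × 0.2 × 0.8/100) = 0.057; 95% range ±1.96 × 0.057 = ±11.1 points.
- p = 0.5: √(2 × 0.5 × 0.5/100) = 0.071; 95% range ±13.9 points. The exact binomial probability of a gap of 10 points or more is 0.18, and of 15 points or more 0.04.

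**2. Effect on the primary contrast.** Shift in mean difference = imbalance × carry-over.
- Low end: 0.111 × 30 = 3.3 s.
- High end: 0.139 × 120 = 16.7 s.
- Harsher case: 0.14 × 240 = 33.6 s.
- Carry-over needed to produce 120 s at the edge of the range: 120/0.139 ≈ 863 s per exposed child.

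These are shifts in means, whereas the reported contrast is between medians, so they indicate order of magnitude only.

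**3. Precision lost by ignoring route.** Let route shift extubating time by e within-route SDs. The pooled SD becomes √(1 + p(1−p)e²) within-route SDs. Power at a standardised difference of 0.4 with 100 per arm is Φ(0.4 × √50/SD − 1.96), where SD is 1 if route is adjusted for. The n per arm for 80% power is 2 × (1.96 + 0.842)² × SD²/0.4².

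| p | e | pooled SD | power, route ignored | n per arm, route ignored |
|---|---|---|---|---|
| 0.3 | 0.5 | 1.026 | 0.787 | 104 |
| 0.5 | 0.5 | 1.031 | 0.783 | 105 |
| 0.3 | 1.0 | 1.100 | 0.730 | 119 |
| 0.5 | 1.0 | 1.118 | 0.716 | 123 |

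With route adjusted for, power is 0.807 and n per arm is 99 in every row. This uses the normal-theory comparison of means as a stand-in for the rank test.

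**The case against.** The strongest reply is that nothing here is invalid. Sevoflurane is stopped before the intravenous drugs, maintenance names no volatile agent, and the primary clock starts only when the study infusion stops. Unstratified blocked randomisation with an unadjusted test is a legitimate design, and its error rate already allows for chance imbalance. The precision loss is modest, and the reported primary result has p < 0.00001. All of that stands, and it limits the point to interpretability and efficiency.

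A reader might go further and infer that the 120 s versus 240 s contrast is distorted by sevoflurane or says nothing about TIVA. The documents do not support that. If route is independent of arm, the contrast is a valid randomised comparison in the children as treated. The pooled figure would misrepresent both routes only if the lidocaine effect differed by route, and nothing in the documents points to such an interaction.

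A reader might also infer that route was steered by allocation. The plan does not say that cannulation is settled before allocation is known, and it describes no blinding of the anaesthetist. But it ties route only to whether a cannula was placed preoperatively, so dependence on arm is conjecture. Route counts by arm would be the direct check.

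The reply leaves one thing unanswered: route is not reported, so the result for TIVA-only children cannot be recovered from what is given.

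**Conclusion.** The point holds as a worthwhile, low-cost improvement to the design and analysis, not as a flaw that undermines the pooled result. The trial cannot show whether its recovery finding applies to children who had TIVA only. Under the assumed shares and carry-over, chance imbalance would move mean extubating time by roughly 3 to 17 s (about 34 s in the harsher case), so it is unlikely to explain a 120 s difference. Ignoring route could reduce power from 0.81 to between 0.72 and 0.79 at a standardised difference of 0.4, if route shifts recovery by 0.5 to 1.0 SD and 30% to 50% of children are induced by mask.

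These sizes depend on a mask share and a carry-over that the documents do not give. The validity of the pooled comparison rests on route being independent of allocation, which is plausible but not stated.

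**What to change.** **For any trial still to be randomised:** record induction route for every child, settled before allocation is revealed, and run the blocks within the two routes. Compare extubating time, PACU stay and opioid use with a route-stratified test (van Elteren) or with route as a covariate, and report route counts by arm.

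**For this trial:** the document is dated after the stated recruitment window and already contains results, so the randomisation cannot be changed. If route can be recovered from records, show route by arm first. Then give the route-stratified result and the result in children who had no sevoflurane, both as sensitivity analyses labelled post hoc. The pooled result stays primary. If route differs by arm, read both with caution: route may then have followed allocation, and stratifying by it or restricting to one route could itself introduce bias.

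**In the text:** reconcile the title with the two accounts of induction under Patients and Study design. No change to clinical care is proposed.

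**Cost:** one recorded field, a little more analysis and, prospectively, two randomisation lists instead of one. Whether route can be recovered for this trial is not known from the documents. The no-sevoflurane subset also has a wider interval: at an assumed mask share of 20% to 50% it holds 160 to 100 of the 200 children, so at equal variability the interval widens by 1/√0.8 = 1.12 to 1/√0.5 = 1.41 times.

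### Does the primary outcome, extubating time, need a BIS reading at infusion stop or a masking statement before it can be analysed as planned?

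*Combined protocol and SAP*

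**What the plan says.** Under Study design in the Combined protocol and SAP, the primary interval is defined thus: "Extubating time will be defined as the time between discontinuation of the infusion and extubation". It ends on a clinical observation: "The LMA will be removed when spontaneous regular breathing was confirmed". The secondary recovery outcome is defined as follows: "The length of staying in PACU will be defined as time between arrival and discharge time". No criterion is given for stopping the infusion or for PACU discharge.

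Under Intraoperative monitoring, BIS is the measure of anaesthetic depth. It is listed with pressures and heart rate, "and BIS values will be recorded at 5-min intervals during anesthesia". No reading is required at the infusion stop or at LMA removal, and BIS is not a named outcome.

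Allocation is by a computer-generated list in blocks of 4. Masking is not mentioned. The nearest text concerns preparation: "Ketofol and lidoketofol will be prepared in one syringe", and later "Ketofol will be prepared at ratio of 1:4 for induction and 1:7 for maintenance".

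The Statistical analysis section applies one method to all continuous data: "Differences in median values of quantitative variables between the groups of patients will be tested with" the Mann–Whitney U test. The Results then state: "Extubating time was significantly lower in lidoketofol group than in ketofol group (120 s versus 240 s", and report lower propofol and fentanyl use per kg in the lidoketofol arm.

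**The concern.** Time from infusion stop to airway removal depends partly on how deeply the child is anaesthetised when the infusion stops. With no stop rule in the text, that moment appears to be left to discretion. If one arm were lighter at the stop, or were stopped at a different point in the case, the intervals could differ for reasons other than speed of emergence. The Results invite the question, because whole-case propofol and fentanyl were both lower in the arm with the shorter interval.

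The BIS record looks too sparse to settle this, since 300 s between readings exceeds both reported extubating times. The silence on masking adds to the worry. Extubating time starts and ends, and PACU stay ends, at actions that someone aware of the arm could influence. At stake is how far the reported 120 s difference supports the recovery effect in the title.

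**Working it through.** There is no planned figure to reproduce: the document gives 100 children per arm, but no effect size, standard deviation or power.

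**Inputs from the document.** BIS spacing 5 × 60 = 300 s (Intraoperative monitoring). Extubating times 120 s and 240 s; propofol 6.6 versus 7.6 mg/kg; fentanyl 2.1 versus 2.3 µg/kg (Results). 100 per arm (Patients).

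**1. Grid against outcome.** 300/120 = 2.5 and 300/240 = 1.25, so the grid is coarser than both times. But nothing says extubating time is read off the grid. It runs between two events, and its precision does not depend on BIS spacing.

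**2. Age of the last BIS reading.** Assume the stop falls uniformly within the 300 s cycle.
- Range 0 to 300 s; mean 300/2 = 150 s.
- P(age > 120 s) = 1 − 120/300 = 0.60; P(age > 240 s) = 1 − 240/300 = 0.20.
- P(a reading falls between stop and extubation) = T/300: 0.40 for 120 s and 0.80 for 240 s, if recording continues to extubation.

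These treat 120 s and 240 s as fixed for every child, although the plan summarises by medians. More importantly, whether a reading is too old depends on how fast depth changes before the stop, not on how long the child takes afterwards. The document has nothing on that rate.

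**3. Exposure.** Propofol (7.6 − 6.6)/7.6 = 13.2% lower; fentanyl (2.3 − 2.1)/2.3 = 8.7% lower. These are whole-case totals and do not measure depth at the stop. Opioid consumption is itself a named secondary outcome, so lower fentanyl may be part of the treatment effect.

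**4. What a last-BIS comparison would show.** The 95% half-width for a mean difference is 1.96 × SD × √(2/100).

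| Assumed SD (BIS points) | Half-width |
|---|---|
| 5 | 1.39 |
| 10 | 2.77 |
| 15 | 4.16 |

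This covers sampling error in the recorded value only. It omits the drift between that reading and depth at the stop, which cannot be estimated from the document.

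**5. What a stop-timing difference could do.** Suppose there is no drug effect and a systematic between-arm shift passes fully into the interval. The chance of significance at two-sided 0.05 is about Φ(shift/(SD × √(2/100)) − 1.96).

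| Assumed SD | 30 s shift | 60 s shift |
|---|---|---|
| 60 s | 0.94 | >0.99 |
| 120 s | 0.42 | 0.94 |
| 180 s | 0.22 | 0.65 |
| 240 s | 0.14 | 0.42 |

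The SDs and shifts are assumptions, and the formula is for means, whereas the plan uses ranks. The reported difference is 240 − 120 = 120 s, so these shifts would equal 30/120 = 25% and 60/120 = 50% of it. The table shows that the outcome would be sensitive to such a shift; it is not evidence that one occurred.

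**The case for a change.** The best argument for a change is that randomisation makes the arms alike at allocation but does not equalise depth at a time zero that comes later. A reader cannot tell faster emergence from lighter anaesthesia at the stop. Existing records could help cheaply: tabulate the last BIS before the stop by arm, add a rank analysis of covariance adjusting for it, and limit the conclusion to strategies as delivered unless depth proves similar.

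The premise stands; the remedies do not improve the plan.
- The table is harmless description, but it leaves the primary result unchanged and rests on a reading up to 300 s old. Giving each reading's age also needs clock times that the plan does not say are kept.
- The adjusted analysis conditions on a variable the treatment may affect. It could remove part of a true drug effect, and neither a changed nor an unchanged result would separate the explanations.
- Making the wording depend on similar BIS, with no margin for similarity, ties the conclusion to the data.
- Extra BIS readings or coded syringes come too late. The study was scheduled for July to November 2020, and the document, dated 18 December 2020, already reports results.

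The argument on masking is stronger. No role is described for anyone who stopped the infusion, removed the LMA, timed the interval or discharged the child. The one-syringe sentence does not settle it: it can simply mean that the components are mixed together, which fits separate induction and maintenance mixtures and says nothing about coding. That gap is real, but silence is compatible with masked or open conduct.

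**Conclusion.** The observations are correct, but no change to the plan follows. On BIS there is no gain. The 300 s grid bears only on what can be said about depth at the stop, and the plan's question, which mixture gives a shorter interval as delivered, does not require equal depth. The randomised Mann–Whitney comparison answers that question. The 120 s difference should be read in those terms, with any effect on drug use or depth included.

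On masking, timekeepers and criteria, the document leaves out detail that the authors can supply when they report the trial. If those staff were not masked, the trial should be described as open-label and the extubating-time and PACU conclusions qualified accordingly. That is a description of what happened and alters neither outcome, test nor sample.

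No figure here measures a bias. The ages of the BIS readings assume random stop times, and the false-positive chances of 0.14 to above 0.99 assume both the shift and the SD. That the stop was at staff discretion is an inference from the absence of a rule.
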